5.2.1.2 Dose Administration

Treatment cycles consist of daily oral dosing of vorinostat (Days 1 through 14) and intravenous dosing of pembrolizumab (Day 1, Cycle 1). The two-drug regimen will be given every 3 weeks. The starting dose of vorinostat will be 100 mg orally QD per day for Days 1 through 14. The dose of pembrolizumab will be 200 mg IV on Day 1, every 21 days.

5.2.1.3 Definition of Dose-Limiting Toxicity (DLT)

DLTs include any Grade 3-5 toxicity related to vorinostat or pembrolizumab during the combination phase only (Cycle 1) (except for a \ge Grade 3 decrease in lymphocytes). Grade 3 nausea or vomiting should be considered a DLT only if unresponsive to therapy and \ge 72 hours in duration. Patients must have taken at least 4 of the 14 doses of vorinostat to be considered evaluable for DLT determination. Patients who do not complete the first cycle of combination therapy during the dose finding phase will be replaced. Patients who do not receive at least 75% of the expected dose of vorinostat due to toxicity are considered to have DLT. Delay in treatment due to a toxicity greater than 2 weeks is also considered a DLT. ALT $>3\times$ ULN + Total bilirubin $>2\times$ ULN will be a DLT which results in permanent drug discontinuation.

3 patients will be enrolled at dose level 1:

- If 1 DLT occurs in the first 3 patients, expand dose level 1 to 6 patients.
- If 0-1 DLT occur in 6 patients, expand to dose level 2.
- If 1 DLT occurs in the first 3 patients, expand dose level 2 to 6 patients.
- If \ge 2 DLTs occur in the 3-6 patient cohort at dose level 2, the lower dose level will be considered the MDT.
- If \ge 2 DLTs occur in the 3-6 patient cohort at dose level 1, the study will be terminated.

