2.0 TRIAL DESIGN

2.1 Trial Design

This is a Phase I/Ib, open-label, safety, and pharmacodynamics study of pembrolizumab in combination with vorinostat in patients with advanced prostate, renal or urothelial cell carcinoma. This clinical study will be composed of a Dose Finding Phase and an Expansion Phase. The Dose Finding Phase will estimate the Recommended Phase II Dose (RP2D) in patients with advanced renal and urothelial cell carcinoma patients. The Dose Finding Phase will lead to the identification of an Expansion Test Dose for pembrolizumab in combination with vorinostat. The Expansion Test Dose will be the Recommended Phase II Dose (RP2D) (i.e. the highest tested dose that is declared safe and tolerable by the Investigators and Sponsor). Patients will be treated with oral vorinostat every day for 14 days, and with

Schema A: Combination Phase

pembrolizumab at the fixed dose of 200 mg IV. Each cycle is every 21 days. Two dose levels of vorinostat will be tested in 2-patient cohorts according to the 3 + 3 standard design (100 mg and 200 mg). 200 mg dose represents 50% of the recommended vorinostat dose as single agent.

For the Dose Finding Phase (Combination Phase, Schema A), the starting dose level of vorinostat will be 100 mg by mouth (PO) every day for 14 days, with 7 days break. The first dose level will have a minimum of 3 patients treated (unless the first 2 patients experience DLTs before the 3rd patient is enrolled).

[figure not shown]
DLTs are defined as Grade ≥ 3 hematological/non hematological toxicities attributable to vorinostat and/or pembrolizumab during the first 21 days of the combination treatment (days 1-21). If DLTs occur in 1 patient treated at the starting dose level a minimum of another 3 patients will be treated at this dose level. If a DLT occurs in more than 1 patient in the first 6 patients the study will be terminated. If a DLT occurs in $\leq 1/6$ patients, 3 additional patients will be treated at the next dose level (level 2) with 200 mg vorinostat PO. If no DLTs occur at dose level 2, this dose level will be recommended for the expansion cohorts of the study. Patients who experience Grade ≥ 3 toxicity and recover to \leq Grade 1 (or to pretreatment baseline level toxicity) may continue treatment at the next vorinostat lower level.

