5.8 Subject Replacement Strategy

Patients who do not complete the first cycle of combination therapy during the dose finding phase will be replaced. Patients who cannot complete Cycle 1 of the expansion phase for reasons unrelated to the study drug will also be replaced.

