8.4 Sample Size, Accrual and Study Duration

A minimum of 51 and maximum of 57 subjects (3-6 per 2 dose levels in the escalation phase + 45 in three expansion cohorts) will be enrolled in this study. The primary sample size is dictated by the 3+3 design described earlier. Subjects not DLT evaluable in the finding phase will be replaced. Three expansion cohorts of up to $n = 15$ subjects each will be used to measure efficacy endpoints and is critical for the planning of the next phase of investigation. Having at least 12 patients per expansion cohort is adequate for the purposes of estimating effect sizes for larger trials for outcomes that are normally distributed or can be transformed to normality.¹⁰ Increasing to 15 per group will help account for the possibility that a few subjects may not be evaluable for efficacy. Subjects not evaluable for efficacy in the expansion phase will be replaced. A subject is not evaluable for efficacy if they do not have at least one follow-up assessment of disease status after completing 1 cycle of combination

therapy. This could be either a scan or an assessment of symptomatic deterioration. Accrual is expected to take up to 12 months.

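### Dose finding: the DLT, evaluability and replacement rules overlap, and no rule keeps a replaced patient's DLT in the 3+3 count

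*Combined protocol and SAP*

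**What the plan says.** **What is a DLT.** Section 5.2.1.3 counts related Grade 3-5 toxicity in Cycle 1 of the combination, with exceptions for lymphocyte decrease and for some nausea and vomiting. It sets no minimum number of doses for this. It adds an exposure rule: "Patients who do not receive at least 75% of the expected dose of vorinostat due to toxicity are considered to have DLT". A combined ALT and bilirubin rise "will be a DLT which results in permanent drug discontinuation".

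**Who is evaluable.** The same section states: "Patients must have taken at least 4 of the 14 doses of vorinostat to be considered evaluable for DLT determination".

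**Who is replaced.** Sections 5.2.1.3 and 5.8 carry the same sentence: "Patients who do not complete the first cycle of combination therapy during the dose finding phase will be replaced". Section 8.4 adds: "Subjects not DLT evaluable in the finding phase will be replaced". None of these excepts a patient who had a DLT. For expansion, Section 5.8 does set a limit by cause: "Patients who cannot complete Cycle 1 of the expansion phase for reasons unrelated to the study drug will also be replaced".

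**What the count decides.** For dose level 1, Section 2.1 says: "If a DLT occurs in more than 1 patient in the first 6 patients the study will be terminated". At level 2, Section 5.2.1.3 falls back to the lower level if two or more DLTs occur. Section 2.1 asks for at least three patients at the first level "unless the first 2 patients experience DLTs before the 3rd patient is enrolled".

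**The concern.** A patient stopped by toxicity after 0 to 3 vorinostat doses satisfies the DLT definition and fails the evaluability test in the same paragraph. Section 8.4 then calls for a replacement. Nothing says which rule prevails, or whether the DLT stays in the count once the patient is replaced.

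The Cycle 1 completion sentences raise the same question for a wider group. A patient stopped by toxicity after 4 to 10 doses is evaluable and a DLT, but may also not have completed the cycle and so be replaced, again with no statement that the DLT is kept. The protocol uses a limit by cause in expansion, so its absence in dose finding is noticeable.

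The count rests on 3 to 6 patients per level. One DLT can separate passing from stopping at level 1, and can decide which dose goes to expansion. Dropping a DLT can only favour passing.

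**Working it through.** **Inputs.** 14 vorinostat doses per cycle, the 4-dose minimum and the 75% rule (5.2.1.3). 3 to 6 patients at each of two levels plus 45 in expansion (8.4). A 33% DLT rate, which Section 8.10 treats as excessive, used here as the true rate p. The share f of DLTs that are dropped is not in the documents; 5% and 10% are assumptions.

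**1. The plan's own figure.** 3 × 2 + 45 = 51 and 6 × 2 + 45 = 57, which reproduces the stated range. The formula has no term for replacements.

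**2. Where the rules overlap.** 0.75 × 14 = 10.5, so a toxicity stop with 10 doses or fewer is a DLT.
- 0-3 doses: DLT and not evaluable; replaced under 8.4, and under the Cycle 1 completion rule if the cycle is not completed.
- 4-10 doses: DLT and evaluable; still replaced under 5.2.1.3 and 5.8 if Cycle 1 is not completed.

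**3. Can it happen?** Section 5.2.1.2 gives pembrolizumab on Day 1. Table 4 permanently ends study drug after a Grade 3 or 4 infusion reaction. If that covers both drugs, the patient stops with 0 or 1 vorinostat dose taken. This is the clearest route.

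**4. Effect on one count.** Suppose five patients are treated at level 1, two are stopped by toxicity after 0-3 doses, and three complete without a DLT. With all DLTs counted there are 2, and the study terminates. With the two replaced patients dropped, the count is 0/3 and the level passes.

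**5. Chance that a level passes.** Passing means 0/3, or 1/3 followed by 0/3:

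Pass(p) = (1 − p)³ + 3p(1 − p)⁵

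At p = 0.33: 0.301 + 0.134 = 0.434.

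If a share f of DLTs is dropped and each such patient replaced, the DLT rate among counted patients is p(1 − f)/(1 − pf).
- f = 5%: 0.3135/0.9835 = 0.319; pass chance 0.456 (+0.022).
- f = 10%: 0.297/0.967 = 0.307; pass chance 0.480 (+0.045).

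At p = 0.40 the pass chance goes from 0.309 to 0.330 or 0.351.

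**6. Given that the event has occurred.** Suppose one of the first three patients has a DLT and the other two do not.
- DLT kept: three more patients must be free of DLT, (1 − p)³ = 0.67³ = 0.301.
- DLT dropped and patient replaced: (1 − p) + p(1 − p)³ = 0.67 + 0.33 × 0.301 = 0.769.

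At p = 0.40 the two figures are 0.216 and 0.686.

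Steps 5 and 6 assume independent patients with a common DLT rate.

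**The case against.** The best defence is that replacing a patient is not the same as deleting an event. No section says an observed DLT is removed. Section 5.2.1.3 classifies the toxicity shortfall as a DLT outright, and Section 2.1 speaks of DLTs in patients treated and lets two DLTs count before a third enrolment. Section 8.3.2 puts every dosed patient in the safety analysis. Section 9.2 requires review of all toxicity in each cohort and DSMC approval before more patients are treated. On this view the 4-dose minimum only says when a patient may be called free of DLT. This is the likelier intention, and a careful team would probably count the event. But none of these sections states the rule, and Section 8.4 directs replacement of the non-evaluable without exception. The DSMC would be working from the same text.

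Three limits on the concern stand.
- Other routes to a stop within three doses are weak. The Schedule of Assessments shows no chemistry between Cycle 1 Day 1 and Cycle 2, so the ALT and bilirubin criterion would need an unscheduled test. Diarrhea would have to reach Grade 3 or 4 on loperamide within about three doses, and the protocol's vorinostat adverse event table gives no timing.
- Pembrolizumab is fixed at 200 mg, so an infusion reaction says little about which vorinostat level to choose, although the protocol still counts it as a DLT.
- Section 2.1 says the prostate cohort was added during expansion, so dose finding appears to be over.

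A reader might infer that a DLT was in fact dropped and that the expansion dose is unsound. Nothing in the documents shows that such a patient existed. A reader might also extend the point to expansion. That is not supported: replacement there for not completing Cycle 1 is limited to causes unrelated to study drug, Section 8.10 monitors DLTs over the first 21 days, and its reference to 5.2.1.3 concerns dose finding only.

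**Conclusion.** The contradiction is real and confined to dose finding. For 0-3 doses the text makes the same patient a DLT and not evaluable, then replaces the patient. For 4-10 doses it can replace a patient with a DLT without saying that the DLT is kept. Read literally, an observed DLT can leave a count of 3 to 6 patients. The surrounding sections favour counting but do not settle it.

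The size depends on a frequency the documents do not give. Under assumed shares of 5% and 10%, the pass chance at a true 33% rate moves from 0.43 to 0.46 or 0.48. The move from 0.30 to 0.77 applies only if a sole DLT among the first three patients has occurred and been dropped; it should not be read as the overall effect. Severity is minor to moderate: a text reconciliation plus a check of a count that appears to be complete.

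**What to change.** Reconcile Sections 5.2.1.3, 5.8 and 8.4 so that the minimum-exposure and replacement rules apply only to patients without a DLT, and state that every observed DLT stays in the dose-level count whatever number of doses was taken. Section 2.1 should agree with that wording. This is a counting rule only; it changes no dose, exposure threshold or stopping criterion.

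Then check the dose-finding records for any patient replaced after a toxicity. If there is one, report the dose-level count with that DLT included. If there is none, a sentence saying so closes the matter.

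The cost is a few sentences and one records check. The stated 51 to 57 patients and the schedule do not change, and expansion needs no change.

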5.2 Trial Treatments

The treatment to be used in this trial is outlined below in **Table 2**

Table 2: Trial Treatment

Drug	Dose/Potency	Dose Frequency	Route of Administration	Regimen/Treatment Period	Use
Pembrolizumab	200 mg	Q3W	IV infusion	Day 1 of each 3 week cycle	Experimental
Vorinostat	100-200 mg	QD	oral	Day 1-14 of each 3 week cycle	Experimental

Trial treatment should begin as close as possible to the date on which treatment is allocated/assigned.

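### A patient with no DLT who took only 4 to 10 of the 14 Cycle 1 vorinostat doses for non-toxic reasons can be counted as having tolerated the dose, because the evaluability floor and the replacement rule are not reconciled

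*Combined protocol and SAP*

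**What the plan says.** Four rules in the combined protocol and SAP decide who enters the DLT denominator.

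- **Evaluability floor (5.2.1.3):** "Patients must have taken at least 4 of the 14 doses of vorinostat to be considered evaluable for DLT determination".
- **Replacement for non-completion (5.2.1.3, repeated in 5.8):** "Patients who do not complete the first cycle of combination therapy during the dose finding phase will be replaced". Neither section says whether completion means reaching Day 21 or taking some number of doses.
- **Replacement for non-evaluability (8.4):** "Subjects not DLT evaluable in the finding phase will be replaced".
- **Shortfall counted as a DLT (5.2.1.3):** "Patients who do not receive at least 75% of the expected dose of vorinostat due to toxicity are considered to have DLT". This applies only when toxicity caused the shortfall.

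Table 2 in Section 5.2 schedules vorinostat on "Day 1-14 of each 3 week cycle", so a full cycle is 14 doses. Section 5.2.1.2 adds: "The dose of pembrolizumab will be 200 mg IV on Day 1, every 21 days". Pembrolizumab for Cycle 1 is thus given in full at the start. Section 2.1 sets the DLT window at Days 1 to 21. The escalation rule in 5.2.1.3 includes: "If 0-1 DLT occur in 6 patients, expand to dose level 2". Section 2.1 allows dose level 2 to be recommended if no DLT occurs there in three patients.

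**The concern.** The paragraph treats low vorinostat exposure in two ways. When toxicity causes it, anything under 75% is a DLT. When something else causes it, the only number given is 4 doses. A patient at 4 to 10 doses who stays on study and has no event meets the stated floor, so 8.4 does not call for replacement. Whether 5.2.1.3 and 5.8 do depends on an undefined term. Two sites could classify the same patient differently.

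The error has one direction. A patient who took less drug had less opportunity for a DLT, so counting that patient as a success makes the dose level look safer. With three patients able to settle dose level 2, one such patient is a third of the evidence behind the RP2D, which is then given to up to 45 expansion patients. The expansion stopping table in 8.10 has the same exposure, because it gives no definition of its own for who counts in N.

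**Working it through.** **Plan's own figures first.** Sample size (8.4): 2 × 3 + 45 = 51 and 2 × 6 + 45 = 57, as stated. Stopping table (8.10): the boundary is the smallest r with P(X ≥ r | N, 0.33) < 0.10. For example N = 6, r = 4 gives 0.097; N = 13, r = 7 gives 0.099; N = 15, r = 8 gives 0.084. Every row from N = 3 to 15 reproduces.

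**The unregulated band.** The floor is 4/14 = 28.6%. The 75% mark is 0.75 × 14 = 10.5, so 11 whole doses (11/14 = 78.6%). The band without a clear rule is 4 to 10 doses, 28.6% to 71.4% of planned vorinostat.

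**What it means in drug.** At dose level 2, 4 to 6 doses give 4 × 200 = 800 mg to 6 × 200 = 1,200 mg in the cycle. A fully dosed level 1 patient takes 14 × 100 = 1,400 mg.

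**Effect on the 3+3.** A level clears with 0 DLTs in 3, or with 1 in 3 followed by 0 in the next 3:

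P(clear) = P(0 of 3) + P(1 of 3) × P(0 of 3).

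Assumption, not in the documents: DLT hazard is proportional to vorinostat doses taken, so risk at 4 doses is p4 = 1 − (1 − p)^(4/14). Take p = 0.33, the threshold in 8.10; then p4 = 1 − 0.67^(4/14) = 0.108.

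- Full exposure: 0.67³ = 0.301; 3 × 0.33 × 0.67² = 0.444; 0.301 + 0.444 × 0.301 = **0.434**.
- One 4-dose patient in each three: P(0) = 0.892 × 0.67² = 0.400; P(1) = 0.108 × 0.67² + 0.892 × 2 × 0.33 × 0.67 = 0.443; 0.400 + 0.443 × 0.400 = **0.578**.
- All patients at 4 doses: 0.892³ = 0.709; 3 × 0.108 × 0.892² = 0.258; 0.709 + 0.258 × 0.709 = **0.892**.

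The same calculation over a range of true rates:

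| True DLT rate at full exposure | Full exposure | One of three at 4 doses | All at 4 doses | One of three at 11 doses |
|---|---|---|---|---|
| 20% | 0.709 | 0.804 | 0.961 | 0.737 |
| 33% | 0.434 | 0.578 | 0.892 | 0.473 |
| 40% | 0.309 | 0.455 | 0.842 | 0.347 |
| 50% | 0.172 | 0.298 | 0.752 | 0.202 |

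The last column shows what an 11-dose floor leaves: at 33%, a rise of about 4 percentage points instead of 14.

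**Effect on the expansion table.** Four DLTs stop a cohort at N = 4 to 6 but not at N = 7, where five are needed. If one under-exposed patient without an event is counted before the fourth DLT, 4 of 6 becomes 4 of 7 and the cohort continues.

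**The case against.** The best counter-argument is that the 4-dose sentence sets a necessary condition, not a sufficient one. It can operate together with the replacement rule beside it, and if completing the cycle means completing its dosing, the patient described here is replaced. Section 5.6 also requires discontinuation for noncompliance or for intercurrent illness that prevents treatment; a patient discontinued during Cycle 1 would not complete it. This narrows the gap but does not close it. If completion meant all 14 doses, one forgotten capsule would force replacement and the floor of 4 would do no work for a patient without a DLT. Section 5.6 puts no number on noncompliance.

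A reader might infer that a dose level can be cleared on 29% of its planned exposure. The documents do not support that as a description of the design. It needs the lenient reading of completion and every counted patient at the floor. One 4-dose patient among three leaves (4 + 14 + 14)/42 = 76.2% of planned vorinostat. It also concerns vorinostat only, since pembrolizumab is given on Day 1 and DLTs from either drug count. For the same reason the hazard model overstates the effect: it gives pembrolizumab no share of the risk. Nothing in the documents says how often doses are missed.

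Safeguards exist. Section 9.2 requires review of all toxicity and DSMC approval before the next stage, 8.10 monitors expansion continuously, and 2.1 allows the RP2D to be lowered. They are real but partial. Applying the 8.10 table from the third patient on, a 15-patient cohort stops with probability 0.18 at a true rate of 33% and 0.34 at 40%.

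Finally, 2.1 says the prostate cohort was added by amendment during expansion, so dose finding appears to be over. That stands, and it changes what the fix can reach.

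**Conclusion.** The point holds as a conflict between two adjacent rules that leaves 4 to 10 doses, missed for non-toxic reasons, without a clear classification. Where such a patient is counted, the DLT rate can only be biased downward. At a true rate of 33%, one 4-dose patient in each three raises the chance of clearing a level from 43% to 58%; 89% is the extreme with all patients at 4 doses. These figures rest on an assumed hazard proportional to vorinostat doses and are an upper-end illustration, not an estimate.

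A reader might go further and infer that the RP2D objective is unanswered. The documents do not show that: they do not report how many doses the dose-finding patients took, and if all took 11 or more, this rule affected nothing. The point should be fixed; it does not rise to a critical defect.

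**What to change.** Reconcile the two sentences in 5.2.1.3, and align 5.8, 8.4 and 8.10 with the result. Suggested wording: *A patient without a DLT is evaluable for DLT only if at least 75% of planned Cycle 1 vorinostat doses (11 of 14) and the Cycle 1 pembrolizumab dose were received and the 21-day window was completed. Other patients without a DLT are left out of the DLT denominator and, in dose finding, replaced. Any patient with a DLT remains in the denominator.* The 75% figure is one the paragraph already uses, though only for toxicity-related shortfall; adopting it here is a choice. If the sponsor prefers another, it must still define completion of the first cycle and say which rule governs.

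Because dose finding appears complete:

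1. Apply the rule to any further DLT evaluation, including N in the 8.10 stopping table.
2. Re-tabulate the dose-finding DLT results with each patient's Cycle 1 vorinostat doses, and state whether the RP2D decision holds under the 75% rule.

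This is an analysis-set rule and changes no patient's treatment. Dose counts are already in the drug diaries (7.1.1.7, 14.4). The cost is a short amendment, one table, and an occasional replacement or slightly smaller DLT denominator.

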5.2.1.4 Supportive Care Guidelines

Note: there is an overlap in potential toxicity related to diarrhea.

If the patient has diarrhea (loose stool) = Grade 2, follow the supportive care guidelines for Vorinostat below. If the patient has diarrhea (loose stool) \ge Grade 3, follow the supportive care guidelines for Vorinostat below.

If a patient has colitis (diarrhea with abdominal pain, mucus or blood in stool) \ge Grade 2, follow the supportive care guidelines for Pembrolizumab below.

Vorinostat: Because vorinostat's dose limiting toxicities are anorexia, dehydration, diarrhea, and fatigue, patients should maintain adequate fluid and food intake. Patients will be encouraged to seek a nutritional consult, if necessary.

Treat diarrhea promptly with appropriate supportive care, including loperamide. Instruct patients to begin taking loperamide at the first signs of:

- Poorly formed or loose stool
- Occurrence of more bowel movements than usual in one day, or
- Unusually high volume of stool.

Loperamide should be taken in the following manner: 4 mg at first onset of diarrhea, then 2 mg after each unformed stool. Daily dose should not exceed 16 mg/day. Loperamide should not be taken prophylactically. Advise patients to drink plenty of clear fluids to help prevent dehydration caused by diarrhea. Avoid loperamide if there is the presence of blood or mucus in the stool or if diarrhea is accompanied by fever. If grade 3 or 4 diarrhea develops on loperamide, discontinue further treatment with vorinostat.

Pembrolizumab: Supportive care guidelines for pembrolizumab can be found in Appendix 14.5.

